the literature showing that one-off trainings are ineffective, and providers require on-the-job training with supervision and feedback. First, providers (study staff members) are taught to use the evidence-based CBT elements in varying combinations of elements, order and dose to address multiple areas such as violence, substance use, mental or behavioral health problems, and skills deficits that affect HIV care (e.g., healthy decision making, adherence). Within the providers, 2-4 are chosen as local supervisors and receive additional training on how to supervise. Following the 10 day in-person training, groups of 5-6 providers meet each week with one of the local CETA supervisors for approximately 2 hours to review cases, present problems, and decide which treatment elements should be used for each individual. Each local supervisor has weekly calls with CETA trainers for supervision, trouble shooting and further capacity building.

Counselors will also receive an additional 2-day training by a Master CETA Trainer on administering CETA elements via telephone (i.e., T-CETA). This training includes a review of the adaptations as well as live practice of the element adaptations.

e. CETA Delivery

Patients randomized to CETA will meet weekly with a lay provider or community health worker member of the study staff for about an hour once each week, approximately 6-12 times depending on presentation and symptom level. This can be done at a location of the person's choosing or by telephone if they choose, including the clinic but can also be a private space in the community to make it more convenient and comfortable for the participant. This treatment arm will include SMS reminders of their HIV care appointments, similar to the active control group (described below).

f. CETA for male partners

The rationale for including male partners is two-fold: a) extensive violence literature suggests interventions should focus on both the female and male counterparts to effectively combat IPV, and b) our previous trial showed that CETA can reduce women's experience of IPV by reducing men's hazardous alcohol use and aggression.

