- Cost and cost-effectiveness: We will estimate the incremental cost-effectiveness of CETA versus active control in achieving the primary study outcome, retained in care and virally suppressed by 12 months, from the provider perspective. If found to be effective, a budget impact analysis will be conducted to estimate the affordability of routine implementation of the intervention at scale.
- Perceptions and acceptability of CETA: Using qualitative focus group discussions and in-depth interviews with both study participants in the treatment arm, CETA providers and healthcare providers. we will also explore the perceptions, acceptability and durability of the intervention, both as a recipient of care and provider and also the feasibility of delivering this intervention which will help inform recommendations for further implementation and scale up of the intervention, which will help inform recommendations for further implementation and scale up of the intervention.

c. Sample Size

Based on the ENHANCE study(85), we estimate that only 40% of those who are unsuppressed will be retained in care and virally suppressed 12 months post-baseline in the control arm. We believe a 20% increase in the percent suppressed and retained between the CETA and control arms would be clinically meaningful. Our primary aim is to analyze the impact of CETA in the full population; however, we have calculated our sample size to ensure our ability to detect differences separately among women who include a partner. With 80% power and 2-sided $\alpha=0.05$, using a chi-squared test for independent proportions our sample size required is 91 per arm (182 total). To have power to detect mediators and moderators (Aim 2), we will increase the sample size to **400 total** with a minimum of 75 women in the CETA arm who include partners (max of 100), which will give us 80% power to detect an absolute 21% difference between arms in women with partners. To get 75 women who include partners in the CETA arm we will have to randomize about 150 women willing to include a partner if randomized to CETA. We will also include at least 75 partners of women, up to 100.

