Themba Lethu clinic alone has about 4000 female patients, while other clinics have similar numbers of patients. Of these, about 1000 had an unsuppressed viral load in the past year. We anticipate that 50% of those we screen will be eligible for the study and of those 50% will enroll. We therefore estimate we will need to **screen approximately 1600 patients** over 18 months, requiring us to screen about 20 patients and enroll approximately 5 patients per week over the enrollment period.

Given we are randomizing 400 women and including up to 100 men, the total sample size for the IRB will be 500.

The IPV literature strongly suggests that more needs to be done with perpetrators of violence (not just survivors), and we know from studies like ours in Zambia that helping male partners led to many positive changes on outcomes, and from the perspective of the women. However, for this study, we wanted the choice to be the womans' – for ethical and safety reasons. Therefore, we could not confirm the ultimate number of male participants we would have.

Sample Size – Qualitative Study Component

For the FGDs and IDIs we will purposively select participants from the main study. We will recruit a total of 40 participants from the treatment arm who completed the trial in 2023. There will be 3 FGDs, with 6-10 participants in each FGD, and 10 IDIs with study participants. We will also recruit 5 CETA providers and 5 healthcare providers who supported referral to CETA from Themba Lethu Clinic and Zola clinic (adherence counselors), for in-depth interviews.

d. Primary Analysis

All primary analyses will be by intention-to-treat. The unit of analysis will be the woman. Our primary analysis will be a comparison of risk differences with 95% confidence intervals. If we identify differences (RD) in baseline covariates we will conduct an adjusted linear regression to get an adjusted RD.

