We will analyze direct effects of CETA on continuous secondary outcomes (e.g., IPV [via SVAWS], mental health [via CES-D and HTQ], and substance use [via ASSIST score]) using linear mixed models. Fixed effects will include treatment arm, time, and arm X time interactions. Random effects will include participant ID to account for repeat measures. We will calculate robust standard errors. The models will estimate the difference in mean symptom change from baseline to each post-assessment between the treatment groups. The difference in mean change will be standardized to calculate Cohen's d effect size.

e. Moderator Analysis

In addition to main effects for the primary and secondary outcomes, we will evaluate the impact of potential moderators (e.g., lack of viral suppression, partner involvement, age, ethnicity, HIV knowledge and attitudes, education, physical health, duration on treatment, presence of side effects, regimen) on suppression and retention and mental health outcomes. An interaction between the moderator and treatment arm will be included in models described above. The interaction term will serve as the coefficient of interest in assessing whether treatment effects varied by levels of the moderator. For the effect of CETA by inclusion of partners we will compare women who included a partner in the CETA arm to those who said they would have included a partner in the control arm. Risk differences will be used to assess effect sizes within moderator levels.

f. Mediator Analysis

We will assess the role of potential mediating variables (IPV, mental health, substance use) on the impact of treatment on our primary outcome to tease out the direct and indirect effects of CETA. Several of the proposed mediators (e.g., interpersonal violence) may reasonably be expected to interact with the treatment arm to impact our primary outcomes. Invalid estimates may occur if this interaction is not considered in the mediator analysis. To allow for the possibility of exposure-mediator interactions, we will use a counterfactual approach and follow methods described by VanderWeele and Vansteelandt(87,88) and Valeri and VanderWeele(89). These methods are appropriate for both

continuous and binary mediators and outcomes and allow for estimating valid controlled direct effects as well as natural direct and indirect effects.

g. Cost Effectiveness Analysis and Budget Impact Analysis

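### The analysis makes no allowance for correlation between women who share a CETA provider; if that correlation is positive, the confidence intervals would be too narrow

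*Combined protocol and SAP*

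**What the plan says.** **Delivery.** Under e. CETA Delivery, each woman in the CETA arm meets a lay provider or community health worker weekly, about 6 to 12 times. The Rationale section leaves the choice, order and dose of elements to the provider. The section on CETA training and supervision has 2 to 4 of the providers acting as local supervisors, and "groups of 5-6 providers meet each week with one of the local CETA supervisors". No total number of providers is given. Under g. Study Arms: Active control, control women receive text reminders and no CETA sessions.

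**Sample size.** DATA ANALYSIS, c. Sample Size, rests on independent observations: "using a chi-squared test for independent proportions our sample size required is 91 per arm (182 total"). No ICC or design effect appears.

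**Analysis.** In DATA ANALYSIS, d. Primary Analysis, the woman is the unit of analysis and "Our primary analysis will be a comparison of risk differences with 95% confidence intervals". For the continuous secondary outcomes (violence, depression, trauma and substance-use scales) the plan specifies linear mixed models: "Random effects will include participant ID to account for repeat measures". The next sentence adds robust standard errors without saying at what level they are clustered. Neither the primary nor the secondary analysis has a provider term, and no sensitivity analysis for provider clustering is described.

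**The concern.** This is a partially nested design: women are grouped under providers in one arm and stand alone in the other. If providers differ in skill, style or choice of content, women with the same provider will have more similar outcomes than women with different providers. The CETA-arm mean then carries between-provider variation that an analysis of independent women leaves out.

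The participant random effect handles repeated measurements on one woman. It does nothing for correlation between women. At stake are the width and coverage of the 95% interval for the primary risk difference, and of the intervals for every scale outcome.

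**Working it through.** **1. The plan's own figure.** Inputs: control proportion 40% ("only 40% of those who are unsuppressed will be retained in care and virally suppressed"), a 20-point difference ("We believe a 20% increase in the percent suppressed and retained between the CETA and control arms would be clinically meaningful", read as absolute), 80% power, two-sided 0.05. The unpooled formula gives (1.960 + 0.842)² × (0.24 + 0.24) / 0.20² = 94.2, so 95 per arm; the pooled formula gives 97. The stated 91 is not reproduced, and 91 per arm gives 77.4% power. That is a separate matter. What counts here is that the calculation contains no design effect.

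**2. Inputs for the clustering check.**
- From the plan: 400 women at 1:1 allocation, so 200 per arm; 40% versus 60%.
- Assumed: k = 10 to 24 providers. This multiplies 2 to 4 supervisors by groups of 5 to 6 (2 × 5 = 10; 4 × 6 = 24), taking every supervisor to run one full group. Equal caseloads m = 200/k.
- Assumed: ICC 0.02 to 0.05. The documents give no value.

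**3. Formulas.** Design effect in the CETA arm: DE = 1 + (m − 1) × ICC. The outcome variance is the same in both arms (0.4 × 0.6 = 0.6 × 0.4 = 0.24), so the correct SE divided by the SE that ignores providers is √((DE + 1)/2). The true size of the nominal 5% test is 2 × [1 − Φ(1.96/ratio)]. Ignoring providers, the 95% half-width is 1.96 × √(0.24/200 + 0.24/200) = 9.6 percentage points.

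| Providers (women each) | ICC | DE | SE ratio | Half-width, points | True size |
|---|---|---|---|---|---|
| 24 (8.3) | 0.02 | 1.15 | 1.04 | 9.9 | 5.9% |
| 24 (8.3) | 0.05 | 1.37 | 1.09 | 10.4 | 7.2% |
| 12 (16.7) | 0.02 | 1.31 | 1.08 | 10.3 | 6.8% |
| 12 (16.7) | 0.05 | 1.78 | 1.18 | 11.3 | 9.7% |
| 10 (20) | 0.02 | 1.38 | 1.09 | 10.5 | 7.2% |
| 10 (20) | 0.05 | 1.95 | 1.21 | 11.7 | 10.7% |
| any | 0 | 1.00 | 1.00 | 9.6 | 5.0% |

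The size column supposes that providers differ but that their effects average to zero.

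**4. Would the planned robust standard errors cover it?** A simulation of 4,000 trials used a continuous change score, provider effects in the CETA arm only and heteroscedasticity-robust standard errors at the level of the woman. With 10 providers the rejection rate under no average effect was 4.9% at ICC 0, 6.5% at ICC 0.02 and 10.5% at ICC 0.05. Robust standard errors at that level do not remove the problem.

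**5. Power.** With 10 providers and ICC 0.05 the SE is 0.0490 × 1.214 = 0.0595. Power for 20 points is Φ(0.20/0.0595 − 1.96), about 92%, against 98% when providers are ignored.

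**The case against.** **The size is assumed.** The documents give neither an ICC nor a provider total, and they describe features that could hold provider differences down: supervision groups that decide elements case by case, weekly trainer review, manualised steps, and repetition of missed steps. If CETA had no effect in any woman's case, provider differences caused by the treatment would vanish too. All of this stands, and it makes the conclusion conditional.

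**The primary outcome is remote from the provider.** Viral load comes from routine laboratory records and is accepted up to 18 months, long after about three months of sessions. The ICC is probably smaller there than for the symptom and violence scales that CETA targets directly. This also stands.

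**Robust standard errors are planned.** They would help only if clustered on provider. The plan does not say so, they appear only with the secondary models, and with few providers they would still need a small-sample correction.

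**Stronger readings that the documents do not support.**
- A reader might infer that the intervals are too narrow as a matter of fact. That requires a positive ICC, which nothing in the plan establishes.
- A reader might take the five CETA providers to be interviewed as the whole workforce, which on the same formulas makes the SE 18% to 40% larger. Five is a qualitative sample, limited to providers active since implementation and in 2023. It is not a staffing figure.
- A reader might assume that each woman's provider is already on file. The fidelity section says that sessions and case details are documented, but the list under Intervention records has no provider identifier, and nothing says that a woman keeps one provider throughout.

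**Conclusion.** The omission is real: neither the primary nor the secondary analysis has a provider term or a stated provider-level variance. Its consequence is conditional. If the ICC is positive and inference is meant to reach beyond these particular providers, as the scale-up aim under Potential Benefits, b. Policy, implies, the 95% intervals would be too narrow. If the ICC is zero, they are correct as planned.

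Under the assumed range the shortfall in the SE is about 4% to 21%, and a nominal 5% test runs at about 6% to 11%. The main comparison is not undermined, since the full sample has power to spare for 20 points. The point matters most for the scale outcomes. It is a worthwhile, inexpensive improvement.

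**What to change.** 1. **Check the data first.** The sponsor should confirm that each woman's provider can be recovered from the session and supervision records. Assign a woman who changed provider to her first provider.
2. **Secondary mixed models.** Add a provider random intercept that applies in the CETA arm only, next to participant, with small-sample degrees of freedom (Kenward-Roger or Satterthwaite). If robust standard errors are kept, state that they are clustered on provider and corrected for few clusters.
3. **Primary risk difference.** Report the 95% interval with provider-clustered standard errors and a small-sample correction. Treat each control woman, and each CETA woman who never started sessions, as a cluster of one, so that the intention-to-treat population is unchanged.
4. **Reporting.** Give the number of providers, the caseloads and the estimated ICC for each outcome.

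**Cost.** A paragraph in the analysis plan, a few lines of code and a data-linkage check. One-year follow-up is complete, so the link must come from existing records; if it was not kept, the work is larger and the gap should be reported as a limitation. Intervals will be somewhat wider.

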At the clinic, study staff will have a randomization code within the tablet system used for data collection. Following completion of the baseline assessment, the computer will generate the next randomization group. Randomization will be blocked to ensure that roughly equal numbers end up in each arm. The computer will also generate the randomization assignment for the Randomization ID assigned to the patient (and subsequently linked with their Screening ID). Randomization IDs and assignments will be generated *a priori* by a U.S.-based study team member and linked into the computer system. We will inform the participant of their assignment immediately after the baseline assessment. Those participants who are assigned to CETA will then be asked whether they want to invite a partner and if so, will be given the information sheet and forms to be completed and returned by their partner. Because randomization will occur only after the baseline assessment, some subjects may drop out before randomization, which will be tracked.

k. Study Arms: Common Elements Treatment Approach (CETA)

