For women who choose T-CETA we will work with them during the initial in person session to determine ways to keep them safe. We will discuss the risks associated with T-CETA to ensure they have a clear understanding of the potential for their conversations to be overheard and the risk for violence should an abusive partner hear the conversation. This session will include planning to ensure they have a safe and private place to be when in T-CETA sessions, having the option for the participant to contact the team using a free “call me” text message to inform the counsellor they are ready and in a safe place if they choose and ways that any communications between the counselor and the participant can be coded to ensure privacy. For example, rather than asking, "are you in a safe and private space for today's session?" the counselor might use an initial coded question tailored to that participant associated with several possible benign responses, determined in advance, to indicate "YES" I am alone, it's ok to continue, or "NO" I can't talk, with an exit strategy planned as well. The safety plan will also include a pre-determined plan to decide what will happen if the counsellor hears voices in the background, or the participant's tone of voice changes, etc. These can include changing the topic of conversation or ending the conversation completely and then later rescheduling the session.

We will end each T-CETA session with a plan for determining the success of the T-CETA approach and any plans to change to in person CETA. This can be done in coded form if the participant wants.

j. Follow-up and Retention

There will be four data collection points: baseline, and 3, 12, and 24 months post baseline. For a purposively selected sample of those participants (n=40) who completed the intervention in 2023 there will also be a qualitative data collection point around 24 months (+/- 3 months) post intervention. Electronic medical records will be obtained to assess our primary outcome. This data collection will be completed in-person. We will assess, violence, mental health and substance use at 3 data collection points: baseline, 3 months post-baseline (the approximate length of CETA treatment and again at 12 months (Figure 2). Because our primary outcomes are retention based (retention and viral suppression) we have no plan to retain patients in the study beyond outreach to complete the CETA intervention. Any effort to do so would undermine the results of the trial.

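### For the mental-health scores, the moderator rule names an arm-by-moderator term that, read literally, averages in the pre-randomisation visit and estimates two thirds of the follow-up moderation

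*Combined protocol and SAP*

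**What the plan says.** DATA ANALYSIS, section d (Primary Analysis) fits the continuous secondary outcomes with linear mixed models. On the structure it says: "Fixed effects will include treatment arm, time, and arm X time interactions". It adds: "Random effects will include participant ID to account for repeat measures", and "We will calculate robust standard errors". It then states what the models are for: "The models will estimate the difference in mean symptom change from baseline to each post-assessment between the treatment groups".

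Section e (Moderator Analysis) applies to retention and suppression and also to mental-health outcomes. Its rule is "An interaction between the moderator and treatment arm will be included in models described above", followed by "The interaction term will serve as the coefficient of interest in assessing whether treatment effects varied by levels of the moderator". No term combining arm, time and moderator is named anywhere.

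Two design facts matter. On the questionnaires, the Follow-up and Retention section says: "We will assess, violence, mental health and substance use at 3 data collection points: baseline, 3 months post-baseline", with the third point at 12 months. On timing, the Randomization section says: "Following completion of the baseline assessment, the computer will generate the next randomization group".

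**The concern.** In the mixed model of section d the treatment effect is carried by the arm-by-time terms, because the target is a difference in change from baseline. Baseline is therefore one of three outcome rows. An arm-by-moderator term added to that model has no time index. It describes how the arm difference in average level, over all three visits, varies with the moderator.

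Baseline precedes allocation, so for a moderator fixed before randomisation the expected arm difference at that visit is zero at every moderator level. Including it dilutes the quantity of interest. The tested coefficient does not match the plan's own definition of the treatment effect.

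At stake are the moderation results for depression (CES-D) and trauma symptoms (HTQ). Estimates would be too small, and real moderation could be missed.

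**Working it through.** The plan gives no power, effect size or sample size for moderation of the mental-health scores, so there is no figure of its own to reproduce.

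**Inputs**

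- Three questionnaire visits, the first before randomisation (Follow-up and Retention; Randomization).
- 400 women, allocated 1:1 (Sample Size; Full Consent).
- Two-sided 5% test. Sample Size states this for the primary outcome; it is assumed here.
- Assumed: a binary baseline moderator split 50/50, giving 100 women in each arm-by-moderator cell.
- Assumed: moderation d = 0.5 SD at both follow-ups.
- Assumed: unit variance and a common within-person correlation rho, the structure a participant random intercept implies.
- Assumed: complete data, relaxed in step 4.

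**Step 1: what the named term estimates.** With complete data and a random intercept, the time-constant arm-by-moderator coefficient equals the contrast of person means over the three visits. Its expectation is (0 + d + d)/3 = 2d/3. For d = 0.5 this is 0.333. Simulating the written model gave mean coefficients of 0.336 (rho = 0.5) and 0.334 (rho = 0.3). The one-third loss does not depend on rho.

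**Step 2: standard errors.** A difference of differences over four cells of 100 has variance 4/100 = 0.04 times a factor.

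- Named term: variance of a person mean over three visits, (1 + 2rho)/3.
- Three-way contrast (mean of the two follow-ups minus baseline): (1 + rho)/2 + 1 - 2rho = 1.5(1 - rho). Its expectation is d.

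**Step 3: power**, as Phi(estimate/SE - 1.96).

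At rho = 0.5:
- Named term: 0.333/sqrt(0.04 x 0.667) = 2.04, power 53%.
- Three-way contrast: 0.5/sqrt(0.04 x 0.75) = 2.89, power 82%.

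| rho | named term | three-way contrast |
|---|---|---|
| 0.3 | 63% | 68% |
| 0.5 | 53% | 82% |
| 0.7 | 46% | 96% |

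Simulation with robust standard errors gave 54% against 82% at rho = 0.5, and 64% against 68-69% at rho = 0.3.

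The squared ratio of the two signal-to-noise values is 2(1 - rho)/(1 + 2rho). It equals 1 when 2 - 2rho = 1 + 2rho, that is at rho = 0.25; below that the named term has more power than this contrast. Where the three-way contrast has 80% power, the named term falls to 60% at rho of about 0.42.

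**Step 4: other conditions** (rho = 0.5).

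- No moderation: the named term rejected in 5.6% of 2,000 simulated trials, so the test is valid under the null.
- Follow-up missing at random for 15% at 3 months and 25% at 12 months (assumed), d = 0.5: the mean coefficient was 0.299, a 40% loss, with power 44% against 79%.
- Moderation of 0.6 SD at month 3 only: the named term averages 0.6/3 = 0.20, and 0.20/0.163 = 1.22 gives 23% power. The three-way contrast averaged over both follow-ups gives 0.30/0.173 = 1.73, power 41%.

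**The case against.** The best defence is that one generic sentence serves two kinds of model. The sentence after it says the purpose is to see whether treatment effects vary, and section d has just defined the treatment effect for continuous outcomes as a difference in change. An analyst reading both could fit the three-way term unprompted. Section e also ends by reporting risk differences within moderator levels, which suits only a binary outcome and suggests the rule was drafted for that outcome. This stands as an account of what the authors may have meant. It does not remove the point: the text names a two-way term and one coefficient, and applies them to mental health. A half-repair is also possible. If the three-way term is added but the arm-by-moderator coefficient is still read with baseline as the reference visit, it estimates moderation at baseline, which is zero in expectation.

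It is also fair to object that rho, the size of moderation and the moderator split are not in the documents. That stands, so the power loss is conditional. Nor is chance baseline imbalance an argument for the three-way term, which carries such imbalance too, in the opposite direction.

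Four stronger readings are tempting and are not supported:

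- That Aim 2 is compromised. The Summary and the Objectives define Aim 2 by the primary outcome, where an arm-by-moderator term is correct.
- That a loss of 20 points or more is established. It needs rho of about 0.42 or higher.
- That month-3-only moderation would be seen by the three-way approach and almost never by the planned term. Like for like the gap is 23% against 41%. Only a month-3 term chosen for that pattern reaches about 85% (0.6/0.2 = 3.0).
- That moderation of SVAWS and ASSIST is affected. Section e extends the analysis to mental health and does not clearly plan it for violence or substance use.

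**Conclusion.** The point holds on the literal wording. For CES-D and HTQ the named coefficient estimates two thirds of the average follow-up moderation. That fraction is exact for complete data, three visits and a moderator fixed before randomisation; with the assumed missing follow-up the shrinkage reached 40%.

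The effect on power runs from none, or a small gain, at rho of 0.25 or below, through about 5 points at 0.3, to about 29 points at 0.5 (82% less 53%), under the stated assumptions. False positives do not increase.

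This is a secondary analysis for which the plan states no power. It should be corrected, but it does not threaten the trial's main conclusions.

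**What to change.** In section e, separate the two kinds of outcome.

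- For CES-D and HTQ, and any other repeated-measures outcome for which moderation is tested, add moderator-by-time and arm-by-time-by-moderator terms to the mixed model.
- Name the three-way terms at 3 and 12 months as the coefficients of interest, and say whether they are tested jointly, separately or as an average.
- Report the arm difference in change from baseline within each moderator level at each visit.
- Keep the arm-by-moderator term for the primary outcome, which has a single value per woman.

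The cost is a sentence or two of plan text and a few model terms, with no new data or participants. The protocol records that one-year follow-up is complete, so the change should be dated and documented before moderator results are examined.
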